NON-INTERVENTIONAL (NI) STUDY PROTOCOL

Study information

Title	Evaluating reduction of opioid and barbiturate use following rimegepant initiation in the United States		
Protocol number	C4951089		
Protocol version identifier	1.0		
Date	12 November 2025		
EU Post Authorization Study (PAS) register number	EUPAS1000000755		
Active substance	Analgesics, calcitonin gene-related peptide (CGRP) antagonists. ATC code: N02CD06		
Medicinal product	Rimegepant (Nurtec 75mg ODT)		
Research question and objectives	Research question Among US adults with migraine and prior use of opioids or barbiturates, how does the use of opioids and barbiturates change following rimegepant initiation? Specific study objectives include:		
	Primary Objective		
	1. To evaluate changes in opioid and barbiturate utilization patterns after the initiation of rimegepant.		
	Secondary Objectives		
	2. To describe the pre-treatment characteristics of new rimegepant users, including demographics, comorbid conditions, and prior medication use.		
	3. To evaluate changes in opioid and barbiturate utilization patterns after the initiation of rimegepant in the subset of individuals using at least one preventive treatment for migraine		
	4. To evaluate changes in opioid and barbiturate utilization patterns after the initiation of rimegepant in the subset of individuals with		

	problematic opioid use (≥ 3 opioid prescriptions and/or morphine milligram equivalents [MME] above 75 th percentile during preindex period)
Country of study	United States
Author	Redacted

This document contains confidential information belonging to Pfizer. Except as otherwise agreed to in writing, by accepting or reviewing this document, you agree to hold this information in confidence and not copy or disclose it to others (except where required by applicable law) or use it for unauthorized purposes. In the event of any actual or suspected breach of this obligation, Pfizer must be promptly notified.

TABLE OF CONTENTS

1. LIST OF ABBREVIATIONS	5
2. RESPONSIBLE PARTIES	6
3. ABSTRACT	8
4. AMENDMENTS AND UPDATES	10
5. MILESTONES	11
6. RATIONALE AND BACKGROUND	11
7. RESEARCH QUESTION AND OBJECTIVES	12
8. RESEARCH METHODS	12
8.1. Study Design	12
8.2. Setting.	13
8.2.1. Inclusion Criteria	14
8.2.2. Exclusion Criteria	15
8.3. Variables	15
8.4. Data Sources	17
8.5. Study Size	18
8.6. Data Management	18
8.7. Data Analysis	19
8.7.1. Statistical analysis plan	20
8.8. Quality Control	21
8.9. Limitations of the Research Methods	22

1. LIST OF ABBREVIATIONS

Abbreviation	Definition
AE	Adverse Event
AMPP	American Migraine Prevalence and Prevention
CaMEO	Chronic Migraine Epidemiology and Outcomes
CGRP	Calcitonin Gene Related Peptide
CPT	Current Procedural Terminology
EC	Ethic Committee
FDA	Food and Drug Administration
GPP	Good Pharmacoepidemiology Practices
HCPCS	Healthcare Common Procedural Coding System
HIPPA	Health Insurance Portability and Accountability Act
ICD-10-CM	International Classification of Diseases, 10th Revision, Clinical
	Modification
IRB	Institutional Review Board
ISPE	International Society for Pharmacoepidemiology
ISPOR	International Society for Pharmacoeconomics and Outcomes
	Research
MME	Morphine milligram equivalents
МОН	Medication Overuse Headache
NDC	National Drug Codes
NSAIDs	Nonsteroidal Anti-Inflammatory Drugs
PASS	Post-Authorization Safety Study
RWD	Real World Data
RWE	Real World Evidence
Rx	Prescription
SD	Standard Deviation
US	United States

3. ABSTRACT

Title: Changes in opioid and barbiturate use following initiation of rimegepant for migraine in the United States

Version and date: 1.0, 12 November 2025

Main author: Redacted (Pfizer Inc.)

Rationale and background: Although opioids and barbiturates are not recommended in treatment guidelines for migraines, they are nevertheless often prescribed to individuals with migraine, despite the risks of dependence and other harms associated with these medications. Prescribing a migraine-specific treatment (e.g., rimegepant) could reduce the use of opioids and barbiturates among individuals with migraine.

Research question and objectives: Among US adults with migraine and prior use of opioids or barbiturates, how does the use of opioids and barbiturates change following rimegepant initiation? The primary objective is to evaluate changes in opioid and barbiturate utilization patterns after the initiation of rimegepant. Secondary objectives are: (1) to describe the pre-treatment characteristics of new rimegepant users, including demographics, comorbid conditions, and prior medication use; (2) to evaluate changes in opioid and barbiturate utilization patterns after the initiation of rimegepant in the subset of individuals using at least one preventive treatment for migraine; (3) to evaluate changes in opioid and barbiturate utilization patterns after the initiation of rimegepant in the subset of individuals with problematic opioid use (≥ 3 opioid prescriptions and/or morphine milligram equivalents [MME] above 75th percentile during pre-index period)

Study design: This is a retrospective, observational, noninterventional, cohort study using commercially available real-world data (RWD) of adjudicated medical and pharmacy claims from closed-network health insurers in the US. The study will examine data from September 1, 2019, to March 31, 2023.

Population: This study will be conducted among adults in the study database diagnosed with migraine who filled a prescription for rimegepant. The population in this database is broadly representative of those in the US covered by commercial, managed Medicare, or managed Medicaid health plans.

Variables: The primary exposure is initiation of rimegepant, defined by the first prescription fill between March 1, 2020, and October 1, 2022. Outcomes include changes in opioid and barbiturate utilization patterns before and after rimegepant initiation, measured by prescription fills, quantity dispensed, average dose, duration of use, and discontinuation. Key covariates are demographic and clinical characteristics (age, sex, region, comorbidities, chronic pain, prior preventive treatments) assessed during the baseline period.

Data sources: This study will analyze the IQVIA PharMetrics[®] Plus longitudinal health plan database, which includes anonymized, medical and pharmacy claims from closed-network, third-party payers in the US. This database includes commercial, managed Medicare, and managed Medicaid health plans.

Study size: The study database includes 52,591,063 individuals. It is estimated that 45,051 (0.86%) have an eligible first prescription for rimegepant and 4,049 (0.0077%) meet all eligibility criteria.

Data analysis: Number of fills and quantity dispensed (in MMEs for opioids and milligrams for barbiturates) will be assessed in the 180 days before and after the index fill for rimegepant. Changes in key outcomes will be analyzed using generalized linear mixed models adjusted for age, sex, region, chronic pain, comorbidities, and use of preventive treatment for migraine. Subgroup analyses will be conducted among individuals using ≥ 1 preventive treatment and individuals with problematic opioid use (≥ 3 fills or MMEs above 75th percentile).

Milestones: This study was initiated in 2023. Analyses were completed in 2024. A manuscript based on this study was accepted for publication in 2025.

4. AMENDMENTS AND UPDATES

None.

5. MILESTONES

Milestone	Planned Date
Start of data collection	21 August 2023
End of data collection	04 September 2023
Registration in the HMA-EMA Catalogues of RWD studies	15 December 2025
Final study report	01 March 2026

6. RATIONALE AND BACKGROUND

Overall harms of opioids

The harms associated with opioid use are a well-established, global problem^{1, 2}. The US Food and Drug Administration (FDA) requires all opioid medications, including immediate release/short-acting and extended release/long-acting formulations, to carry a boxed warning on the label stating the risk for addiction, dependence, abuse, and misuse, which can lead to overdose and death^{3, 4}.

Opioids for migraine

Opioid use for individuals with migraine is associated with negative outcomes⁵. Frequent use (≥10 days/month for >3 months⁶) of opioids is associated with medication overuse headache (MOH) and an increased risk of progression from episodic to chronic migraine⁷⁻¹⁰; MOH is associated with impaired quality of life¹¹, greater disability¹², and higher healthcare resource utilization^{13, 14}. Evidence also suggests that opioids are not effective for the acute treatment of migraine and their use can impair the effectiveness of other medications used for the acute treatment of migraine (e.g., triptans)^{15, 16}. Clinical practice guidelines for the management of migraine recommend against the use of opioids for the acute treatment of migraine, except in limited circumstances^{3, 17-20}. Nevertheless, patients with migraine are frequently prescribed opioids^{9, 21-24} or use opioids prescribed for other pain conditions to treat their migraines.

Individuals with migraine are more than twice as likely to receive opioids compared with non-migraine controls²¹⁻²⁵. In the American Migraine Prevalence and Prevention (AMPP) study, ~30% of respondents with migraine reported current or previous opioid use⁵. In a retrospective claims analysis of 147,832 people with migraine who initiated preventive treatment, 77.4% also received an opioid for acute treatment during the follow-up period of up to 5 years²⁶. Emergency department visits for migraine frequently result in administration of opioids or their prescription – 20% in Australia²⁴ and 59% in the US²⁷ – and this is associated with increased future health resource utilization²⁸. Nearly 20% of patients presenting to a tertiary care headache center reported they first received opioids in the emergency department²⁹.

Barbiturates for migraine

Barbiturates – primarily butalbital – are often found in analgesics used for headache or migraine, usually in combination with aspirin, acetaminophen, or codeine. A survey of 9128 respondents with episodic migraine in the US found that 6% were using analgesics that contained barbiturates³⁰. Analyses of 3121 respondents in the Chronic Migraine Epidemiology and Outcomes (CaMEO) Study found that 12.8% used analgesics that contain barbiturates²². Similar to opioids, barbiturates can also lead to dependence³¹, contribute to MOH, increase the risk of progressing to chronic migraine^{16, 32}, and are not recommended by clinical practice guidelines for migraine^{18, 19}.

Rimegepant for migraine

Rimegepant is an orally administered calcitonin gene related peptide (CGRP) receptor antagonist approved by the US FDA in February 2020 for the acute treatment of migraine and in May 2021 for the prevention of episodic migraine. Several studies support the effectiveness of rimegepant for the acute treatment³⁴⁻³⁸ and prevention³⁹ of migraine. A previous analysis suggested that individuals who may be using opioids or barbiturates for the acute treatment of migraine might decrease such use after initiating a migraine-specific treatment such as rimegepant³³.

This noninterventional study is designated as a PASS and is conducted voluntarily by Pfizer.

7. RESEARCH QUESTION AND OBJECTIVES

The study aims to address the following research question: Among US adults with migraine and prior use of opioids or barbiturates, how does the use of opioids and barbiturates change following rimegepant initiation? Specific study objectives include:

Primary Objective

1. To evaluate changes in opioid and barbiturate utilization patterns after the initiation of rimegepant.

Secondary Objectives

- 2. To describe the pre-treatment characteristics of new rimegepant users, including demographics, comorbid conditions, and prior medication use.
- 3. To evaluate changes in opioid and barbiturate utilization patterns after the initiation of rimegepant in the subset of individuals using at least one preventive treatment for migraine
- 4. To evaluate changes in opioid and barbiturate utilization patterns after the initiation of rimegepant in the subset of individuals with problematic opioid use (≥ 3 opioid prescriptions and/or morphine milligram equivalents [MME] above 75th percentile during pre-index period)

8. RESEARCH METHODS

8.1. Study Design

This is a non-interventional, retrospective, observational, cohort study that will assess changes in opioid and barbiturate utilization after initiation of rimegepant among adults in the US. This study will analyze an administrative claims database (IQVIA PharMetrics® Plus) with information on

individuals in the US with commercial, managed Medicare, or managed Medicaid health plans. This database includes information captured in medical and pharmacy claims (e.g., dates of service, diagnosis codes, procedure codes, medications dispensed, demographics, health plan enrolment)⁴⁰.

This study aims to characterize, in a real-world setting, the use of opioids and barbiturates among individuals with migraine before and after initiating rimegepant. Individuals will be grouped according to their use of 5 medications prior to rimegepant initiation (index date): 1. opioids, 2. barbiturates (i.e., butalbital), 3. alprazolam, 4. rescue inhalers, or 5. statins. The latter three groups will be used as controls to represent medications intended for continuous use and episodic use.

Rimegepant is approved for both the acute treatment of migraine and the prevention of episodic migraine. For the acute treatment of migraine, rimegepant is taken as needed. For the prevention of episodic migraine, rimegepant is taken every other day. Since the same medication is approved for 2 indications, assumptions must be made about the intended use when analyzing real world data.

Rimegepant is commonly dispensed in packages of 8 tablets. When 2 packages (16 tablets) are dispensed, it is assumed that rimegepant is intended for the prevention of episodic migraine. When 1 package (8 tablets) are dispensed, it is assumed that rimegepant is intended for the acute treatment of migraine.

For each medication of interest, outcome measures will include the total number of prescriptions filled/dispensed, the total quantity dispensed (number of tablets or other medication units), the average dispensed per fill (calculated for opioids in MME and for butalbital and alprazolam in mg), the total duration of use (days supplied), and the proportion of individuals with discontinuation (defined as the absence of any prescription fill in after rimegepant initiation).

This study design is appropriate to the study objectives and allows for the evaluation of real-world prescription medication use patterns in a large group of individuals broadly representative of patients in the US taking rimegepant without influencing patient or provider behavior. Pharmacy claims databases are often used for this purpose, supplemented by medical claims to provide diagnosis codes to help understand why medications are being used and the comorbidities of individuals taking those medications^{41,42}. By utilizing an administrative claims database, the study can efficiently examine the use of prescription medications dispensed by retail pharmacies and similar outlets in a large and diverse population of adults in the US with commercial health plans^{42,43}.

The pre- vs. post- study design is commonly used in non-interventional studies using real world data and allows researchers to examine outcomes of interest before and after an event occurs⁴⁴. Such study designs are unable to establish a causal relationship between the event and outcome and researchers must be cautious to minimize bias and confounding. The use of multiple control groups for medications intended for continuous or episodic use (alprazolam, rescue inhalers, statins) provides relevant comparators and enhances the validity of the findings observed. Study findings might inform future studies focused on how the use of rimegepant for migraine might impact the use of other, suboptimal medications (opioids/barbiturates) often used for migraine.

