8.7. Data Analysis

The workflow below will be applied to conduct data analysis.

- 1. First, all individuals who meet all study eligibility criteria (study population) will be identified.
- 2. Second, all data for the study population will be extracted from the study database into an analytical file that will be used for all subsequent analyses.
- 3. Third, all required study variables will be identified or calculated in the study population.

The Center for Center for Medicare & Medicaid Services (CMS) Opioid Oral MME Conversion Factors Table (available at the US department of Health and Human Services portal) will be used to standardize opioid dose measurements in MME (ie, for each prescription, the daily dose will be multiplied by the corresponding opioid conversion factor and then divided by days supplied; MMEs will be summed across all opioid prescriptions).

- 4. Fourth, all required subgroups will be created in the study population.
- 5. Fifth, study outcomes will be summarized across study subgroups, which are determined by the pharmaceutical form of each medication as summarized in the table below:

Table 2. Study subgroups

	Opioids	Barbiturates	Alprazolam	Rescue Inhalers	Statins
Number of Rx fills	X	X	X	X	X
(mean, SD, % change)					
Tablets/quantities dispensed	X	X	X	X	X
(mean, SD, % change)					
Milligrams dispensed		X	X		
(mean, SD, % change)					
Morphine milliequivalents (MME)	X				
(mean, SD, % change)					

Days supplied	X	X	X	X	X
(mean, SD, % change)					
Discontinuation in post-index	X	X	X	X	X
(mean, SD, % change)					

Subgroups vary according to the dosage form of each medication. Rx: prescription

6. Sixth, statistical comparisons will be conducted according to the Statistical Analysis Plan, described below.

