8.7.1. Statistical analysis plan

- 1. Among each medication use group, a report with descriptive statistics of the demographic and clinical baseline characteristics as well as medication use prior to rimegepant will be created.
- 2. Next, a patient-level dataset containing crude counts of the five utilization outcome measures for each 30-day window (W1-W12) of the pre- and post-index periods will be created.
- 3. To measure changes in utilization outcome measures across the pre-index to post-index period, two aggregated measures for each outcome based on time during the pre- (W1-W6) or post-index (W7-W12) period will be created. Using these aggregate measures, the pre and post-index mean outcome values and determine the percent change (%Δ) will be presented.
- 4. In order to determine the association between rimegepant initiation and reduction of other acute treatments, a generalized linear mixed models for each outcome will be applied. Mixed effects models account for within-person correlation due to the repeated measurement of outcomes over time in longitudinal studies. The main independent (exposure) variable will be a binary indicator of time during the pre-index period (0) vs. post-index period (1). For modeling the continuous and count outcomes—number of fills, quantity dispensed, average dose, and duration of use—first the distribution of each utilization outcome measure within the dataset will be determined in order to specify the appropriate distributions and link functions for their mixed model. The discontinuation outcome is a binary outcome, observed at one point in time. Hence, a logistic regression model to examine any association to rimegepant initiation will be applied. For each model, for pre-index demographic and clinical characteristics, including age, sex, region, presence of any chronic pain (migraine or non-migraine), Elixhauser weighted index, and pre-index use of any prevention agent will be adjusted.
- 5. To determine the robustness of the outcome measures and association estimates, two subgroups and two sensitivity analyses will be performed as described below. The sensitivity analyses only apply to the total cohort, and not the additional subgroups.
 - a) Subgroup analysis #1: Identify all individuals from the total cohort with use of ≥ 1 prevention agent during the pre-index period, presented by medication use group.

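### The control drug groups are said to strengthen validity, but 8.7.1 uses them only descriptively and plans no between-group contrast

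*Protocol*

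**What the plan says.** Section 8.1 groups patients by pre-index use of opioids, butalbital, alprazolam, rescue inhalers or statins. Of the last three it says: "The latter three groups will be used as controls to represent medications intended for continuous use and episodic use". It then concedes that a pre/post design cannot establish cause, and presents the control groups as a safeguard that "provides relevant comparators and enhances the validity of the findings observed".

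Section 8.7 states that "statistical comparisons will be conducted according to the Statistical Analysis Plan, described below", which points to 8.7.1. There, step 3 presents pre and post means and percent change, and Table 2 in 8.7 lists these summaries for all five drug groups. Step 4 is the inferential step. Its purpose is worded "In order to determine the association between rimegepant initiation and reduction of other acute treatments", and for this "a generalized linear mixed models for each outcome will be applied". The exposure is a 0/1 indicator of pre-index versus post-index time. The adjustment set is "age, sex, region, presence of any chronic pain (migraine or non-migraine), Elixhauser weighted index, and pre-index use of any prevention agent". Discontinuation is observed once per patient, and for it "a logistic regression model to examine any association to rimegepant initiation will be applied".

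The last inclusion criterion in 8.2.1 requires at least one pre-index fill of one of the five drugs. No post-index fill of that drug is required.

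**The concern.** The safeguard claimed in 8.1 needs some quantity that sets the change in opioid or barbiturate use against the change in a control drug. Section 8.7.1 contains no such quantity. A reader would see a modelled fall for opioids beside a different change for statins or inhalers and would judge the difference by eye, or by which result reached significance. A difference in significance is not a test of a difference.

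This matters because the within-group period effect is not clean. Patients enter a drug group because they filled that drug in the 180 days before index, so their mean use tends to fall afterwards even if nothing has changed. The covariates are all fixed at baseline and include no calendar time, so secular change also stays in the period term. Step 4 would report the sum of these under a heading that speaks of an association with rimegepant initiation.

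**Working it through.** **1. Where the control groups enter the plan**

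- 8.1: named as controls, with a validity claim attached.
- 8.7, Table 2, and 8.7.1 step 3: pre and post summaries for each group, side by side.
- 8.7.1 step 4, mixed models: period indicator plus baseline covariates. No drug-group term and no group-by-period term.
- 8.7.1 step 4, logistic model: one post-index observation per patient, initiators only. No drug-group term.
- 8.7.1, two subgroup and two sensitivity analyses: they change the population or the window length. None adds a contrast between groups.

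The groups therefore enter the descriptive estimates but no model.

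**2. Size of the entry-rule effect with no drug effect**

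The protocol gives no fill rates, so m (mean fills per 180 days) and the between-patient spread are assumptions.

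*Equal rates (Poisson).* Given at least one pre-index fill, the pre mean is m/(1 − e^−m) and the post mean is m. The ratio is 1 − e^−m, so the change is −e^−m.

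| m | change in mean fills |
|---|---|
| 0.5 | −61% |
| 1 | −37% |
| 2 | −14% |
| 3 | −5% |
| 6 | −0.2% |

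*Rates varying between patients (gamma-Poisson, shape k).* With t = m/k and p0 = (1+t)^−k, the pre mean is m/(1 − p0) and the post mean is [m − m(1+t)^(−k−1)]/(1 − p0). The ratio is 1 − (1+t)^(−k−1). For k from 0.5 to 2 the change is:

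- m = 0.5: −35% to −51%
- m = 1: −19% to −30%
- m = 2: −9% to −13%
- m = 6: about −2%

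The same rule produces apparent discontinuation with no drug effect: 31% to 35% at m = 1 and 5% to 11% at m = 6.

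**3. What a between-group contrast would do, again with no drug effect**

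- Episodic drug, m = 1, k = 1: t = 1, p0 = 0.5, pre = 1/0.5 = 2.0, post = (1 − 0.25)/0.5 = 1.5. Ratio 0.75.
- Control with the same fill pattern: ratio 0.75. Ratio of ratios 0.75/0.75 = 1.00.
- Near-monthly control, m = 6, k = 2: t = 3, p0 = 1/16, pre = 6/0.9375 = 6.4, post = (6 − 6/64)/0.9375 = 6.3. Ratio 0.98. Ratio of ratios 0.75/0.984 = 0.76.

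A simulation with 2,000,000 draws per group gave ratios of ratios of 0.999 and 0.762, in agreement. The contrast removes the artefact against a control with a similar fill pattern and leaves nearly all of it against a near-continuous one.

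**4. How the reported figure could move (assumed values)**

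If opioid fills fell 30% and control fills fell 22%, the period term would give 0.70 and the contrast 0.70/0.78 = 0.90. With a control fall of 10% the contrast is 0.70/0.90 = 0.78, and with 25% it is 0.70/0.75 = 0.93.

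**The case against.** The strongest reply is that the research question in section 7 asks only how opioid and barbiturate use changes after initiation. A within-group period effect answers that directly. This stands: the excess change over a control is not the stated objective, and the within-group estimate should remain. The comparative need comes from the validity claim in 8.1 and the purpose stated in step 4.

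The causal limit is also disclosed, in 8.1 and in item 10 of 8.9. That lessens the harm, but neither place says how the controls enter the inference.

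A separate SAP might contain the contrast. Section 8.7, however, names 8.7.1 as the governing plan, and Annex 1 lists only a data dictionary and table shells. The exposure term is stated, not left open.

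Several stronger readings are tempting but not supported:

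- That the controls are never used. They are tabulated with means and percent changes.
- That a primary test is invalid. The protocol names no primary test, hypothesis or single primary outcome.
- That the controls show what happens in the same patients. Groups are formed by prior drug use. They may overlap, but a statin user need not use opioids, so the contrast is largely between patients and needs a parallel-change assumption.
- That the opioid fall is an artefact. The entry rule pushes mean fills downward, but without fill rates the amount is unknown.
- That the group-by-period term should replace the within-group estimate as the main result. Against a control such as statins it would not remove regression to the mean.

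**Conclusion.** The concern holds in a limited form. The validity claim in 8.1 is not matched by any between-group estimate or test in 8.7.1. The controls support visual comparison only, and the mixed models deliver uncontrolled before/after changes.

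The downward pull from the entry rule needs only that fills vary over time within patients. Its size depends on assumed rates: in the no-effect examples, about −19% to −37% at one fill per 180 days and about −2% or less at six. These calculations assume stable individual fill rates and independent periods, and no document figure shows the actual bias. Secular change is a further component that the documents do not allow one to size.

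**What to change.** Add to 8.7.1 step 4 a supplementary pooled model for outcomes shared by all five groups (number of fills, days supplied):

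- Include group, period and group-by-period terms, with patient-level clustering because a patient may belong to more than one group.
- Report the ratio of post/pre ratios for opioids and for barbiturates against each control separately.
- Name the control with the most similar episodic fill pattern as the relevant comparator. Section 8.1 does not say which control represents which kind of use; the pre-index fill distributions can settle this.
- State the parallel-change assumption, and state that a near-continuous control such as statins does not absorb regression to the mean.
- Keep the within-group change as the answer to the stated objective, labelled an uncontrolled before/after change.
- Label the added contrast post hoc, because the abstract says analyses were completed in 2024.

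If the contrast is not added, withdraw the statement in 8.1 that the controls enhance validity.

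Cost: a few extra models on the patient-by-window dataset already planned in step 2, and probably a smaller apparent reduction. The final study report is planned for 01 March 2026, after the protocol date of 12 November 2025, so the change can still be reflected there.
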